- 23) **Test of Self Conscious Affect – 3 (TOSCA-3)** is a scenario based measure composed of 16 scenarios of potential positive and negative occurrences in work and social arenas of life. It is designed primarily to assess shame and guilt responses but also includes pride. The respondent is asked to respond to several questions following the scenarios indicating the likelihood of reacting in certain ways. Sixteen of the 32 scenarios are presented at baseline.
- 24) **Irritability Question – One question designed to assess participant irritability at the conclusion of completing the questionnaires was added.**

Following completion of the questionnaire packet and the computerized tasks, the participant will be randomized to 1 of 4 groups. All groups will be provided a packet of instructions to guide their participation in the coming weeks, and the packet will be reviewed with the participant by someone on the research team (see Appendix A). Participants in the 3 picture taking groups will also be provided instructions to create a login to the research drive if they do not have an account and will be provided instructions regarding how to upload their photographs to the research drive.

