H5: Participants in the PS and PTPSS conditions will demonstrate significant changes in behavioral indicators of attentional shifts. We anticipate participants in the active experimental conditions will a) take increasingly more photographs over the course of the intervention and b) will include more social behavior as the focal point.

Supplementary Analyses

H6, exploratory: In order to inform future implementation and potential mechanisms of change, we will examine photographic content. We also anticipate changes in the quality of the photographs over the course of the intervention for the participants in both active experimental conditions. It is possible that the photographic content would be judged by independent raters to be increasingly positive over the course of the intervention. Alternatively, it is plausible that as the participant's ability to attune to the positive cues in the environment

develops, the capacity to find joy in even the most mundane objects/moments will be evident in photographs judged by independent raters to have less objectively rated positive appeal.

H7: Depressive symptoms will moderate the associations between intervention participation and daily positive affect, life satisfaction, and perceived social support, such that participants with higher levels of pre-intervention symptoms will show larger improvements in outcomes in the intervention conditions.

H5b and H6 are straightforward between-groups analyses, for which we will use ANOVA to test for significant differences between groups on the outcomes of interest. H1-H3 and H5a will be tested using mixed-factor ANOVA, with condition as a between-subjects factor and the within-subjects factor being pre-intervention measure of the outcome of interest included as predictors of the post-intervention outcome (e.g., perceived social support). Planned contrasts will probe for significant differences in effects between the experimental conditions and each control condition, as appropriate. H7 will be tested using two additional predictors, the main effect of the individual difference of interest (e.g., depressive symptoms) as well as the interaction between the individual difference and condition. H4 (mediation) will be tested using the most up-to-date evidence for bootstrapping estimates (see Hayes; Preacher & Hayes, 2008).

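### H5a and part of H6 predict change during the 21 days, but the tests assigned to them (a pre/post model and a between-groups ANOVA without a time term) do not test that change

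*Combined protocol and SAP*

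**What the plan says.** **Hypotheses.** Under Mediators of Change, H5a predicts that participants in the two experimental conditions will "take increasingly more photographs over the course of the intervention". Under Supplementary Analyses, H6 is labelled exploratory. It opens with a general aim of examining what the photographs show, then adds "We also anticipate changes in the quality of the photographs over the course of the intervention". Two opposite directions are allowed: ratings may become more positive, or photographs may be "judged by independent raters to have less objectively rated positive appeal".

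**Assigned tests.** The analysis paragraph after H7 states "H5b and H6 are straightforward between-groups analyses, for which we will use ANOVA to test for significant differences between groups". H5a goes with H1-H3 to a mixed-factor ANOVA, with "the within-subjects factor being pre-intervention measure of the outcome of interest included as predictors of the post-intervention outcome". It adds: "Planned contrasts will probe for significant differences in effects between the experimental conditions and each control condition, as appropriate".

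**Data.** Under Testing Procedure, baseline consists of 24 listed measures and two computer tasks. Then: "Following completion of the questionnaire packet and the computerized tasks, the participant will be randomized to 1 of 4 groups". The upload instructions follow: "Participants in the 3 picture taking groups will also be provided instructions to create a login to the research drive". Uploads are daily for 21 days. The passive control arm is not asked for photographs, though all four groups complete a weekly survey about taking and sharing pictures.

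**Time-based analysis elsewhere.** The closing paragraph says that daily photographs may be quantified for positivity and social connection, that these may increase over time (citing H5a), and that exploratory growth curves will be run.

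**The concern.** A hypothesis that something changes during a period needs a test with time in it. H6's test has none, and the plan itself sets it apart from the mixed-factor model in the next sentence. H5a's test has a within-subject factor, but it contrasts before with after, not early with late in the intervention.

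For H6, a significant result on average ratings would not show that photographs changed, or which of the two stated directions occurred, and a real change could be missed. For H5a, the within-subject factor is left undefined for the data that the text describes. H5a carries no exploratory label, so the planned test should match its wording.

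**Working it through.** The plan gives no power, effect size or SD for H5a or H6, so there is no figure to reproduce. The main check is textual; the arithmetic is illustration.

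**Hypothesis against test**

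| | Claim | Assigned test | Time within the 21 days? |
|---|---|---|---|
| H5a | count rises during the intervention | pre-intervention value predicting post-intervention value | no |
| H6, change part | rated quality changes, either direction | between-groups ANOVA, outcome undefined | no |
| H6, general aim | describe content | between-groups ANOVA | not needed |
| H5b | more social content | between-groups ANOVA | valid between-arm comparison |

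For H5a, none of the 24 baseline measures or the two tasks is described as a photo count. Randomisation and the drive instructions come after them, and the exit packet lists no count either. Even with a baseline count, a jump on day 1 that then stayed flat would give a pre/post difference without any increase during the intervention.

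**Illustration for H6.** All inputs are assumptions except the total of about 240:
- 240/4 = 60 per arm; three uploading arms; error df 3 × 60 − 3 = 177
- two-sided alpha 0.05
- PT and PTPSS behave alike and are pooled against Document This!
- three weekly scores with equal pairwise correlation ρ, scaled so that the 3-week mean has SD 1
- the same true slope for everyone within an arm

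Variance factor for the contrast: 1/60 + 1/120 = 0.025.

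*Means.* λ = d²/0.025. For d = 0.25, λ = 0.0625/0.025 = 2.5 and power is 0.349. For d = 0.5, λ = 10.0 and power is 0.882.

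*Slopes.* Weekly variance is 3/(1 + 2ρ), and per-person slope variance is (1 − ρ) × weekly variance/2.
- ρ = 0.6: 0.4 × 1.364/2 = 0.273; for 0.25 per week, λ = 0.0625/(0.273 × 0.025) = 9.17; power 0.853.
- ρ = 0.3: 0.7 × 1.875/2 = 0.656; λ = 3.81; power 0.493.

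| Difference from Document This! in weeks 1, 2, 3 (SD) | Contrast on means | Contrast on slopes (ρ = 0.6 / 0.3) |
|---|---|---|
| Rise: 0, 0.25, 0.5 | 35%, positive | 85% / 49%, positive |
| Fall: 0.5, 0.25, 0 | 35%, positive | 85% / 49%, negative |
| Constant 0.25 | 35%, positive | 5% |
| Rise with zero average: −0.25, 0, 0.25 | 5% | 85% / 49% |
| Constant 0.5 | 88% | 5% |
| Plateau: 0, 0.5, 0.5 | 55% | 85% / 49% |

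The first three rows have the same average difference of 0.25, so a test on means cannot separate them. With week as a categorical factor (2 and 354 df), the plateau gives 89% / 51% and the rise 78% / 39%.

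**Sensitivity.** Between-person slope variation lowers the slope figures. With slope SD 0.25 per week at ρ = 0.6, slope variance is 0.273 + 0.0625 = 0.335, λ = 7.46 and power is 78%. With slope SD 0.5, power is 59%. At ρ = 0.3 the figures are 46% and 38%.

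**The case against.** The strongest reply is that the closing paragraph already covers time. It foresees quantifying photographs for positivity, mentions increases, cites H5a and plans growth curves. An exploratory growth curve suits an exploratory hypothesis, and the ANOVA can be read as serving H6's descriptive aim. This has force for H6, and it rules out the inference that the plan has no time-based analysis of photographs. But the quantification is only a possibility, photo count is not named as an outcome, no condition-by-time test is given, and nothing says that these analyses replace the assigned tests.

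Further replies stand in part:
- **H6's outcome is undefined.** An ANOVA on each person's change or slope would be sound. The harm therefore depends on using average ratings, and a reader should not infer that the H6 test must mislead.
- **A photo count may exist elsewhere.** The questionnaire packet and appendices are not in the public text, so it is too strong to infer that the H5a model cannot be fitted.
- **Loose drafting.** A mixed-factor ANOVA could take week as its factor, and the pre/post wording carries a social-support example. The text still defines the factor as the pre-intervention measure. Nor does it follow that the analyst must choose after seeing the data; the factor can be fixed beforehand.
- **No comparator is named.** Neither H5a nor the change statement in H6 names one, so a within-arm time effect would also match the wording. Pooling PT and PTPSS against Document This! is one reasonable choice, not a requirement of the text.
- **The power figures are assumed.** They omit missing uploads and do not model counts. A reader might infer that slopes are generally more powerful; the constant-difference rows show otherwise, as does the plateau at ρ = 0.3 (55% on means, 49% on slopes).

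**Conclusion.** The point holds in limited form. H5a and the change part of H6 are worded as change during the intervention, and the tests assigned to them do not address it. For H5a the mismatch holds whether or not a baseline count exists. For H6 its consequence depends on the rating being averaged over the period, which the plan neither states nor excludes.

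The effect is minor to moderate, but worth fixing before analysis. H6 is exploratory, some analysis over time is already foreseen, and H1-H4 and H7 are unaffected. H5b's between-groups test is sound. The conclusion rests on matching each test to its hypothesis. The percentages only illustrate how level and change can come apart, and they do not set the severity.

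**What to change.** In the analysis paragraph, for H5a and the change part of H6:

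- Replace the pre-intervention factor (H5a) and the between-groups ANOVA (H6) with a longitudinal model of the uploaded photographs in the three uploading arms. Use study week (categorical) or day as the within-subject factor, and a participant random effect.
- Name the time-by-condition term as the test, for example PT and PTPSS versus Document This!, two-sided for H6. Use a count model for H5a.
- Define the H6 outcome (rating scale and unit). State whether a day without an upload counts as zero or as missing.
- State how this relates to the exploratory growth curves in the closing paragraph.
- State that the passive arm is not in these upload-based tests. Its weekly survey on taking and sharing photographs may be reported descriptively.
- Keep the between-groups ANOVA for H5b and for H6's general aim of examining content.

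The cost is a few sentences and slightly more analysis work on uploads already collected, with no new visits, measures or participants. The downside is that a time-by-condition test can have less power than a comparison of means when the effect is an early or constant shift. It also shows that change differed between arms, not why; fatigue or drifting compliance could produce the same pattern.

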- 1) Those participants who are randomized to the active Picture This! savoring condition will be asked to use their Smartphones to take at least two photographs each day for 3 weeks of something that brings them joy or peace and to upload their pictures daily to a drive accessed by study staff (instructions for each condition may be found in Appendix A). Each evening, they will be directed to

complete an online exercise in which they review the photograph(s) taken that day. They are also asked to complete several questions via an internet survey.

- 2) Participants randomized to the Picture This! Plus Social Sharing will do everything as described for the Picture This! group. In addition, each week, they will be directed to share the photos they took during the prior week with a friend or family member (see script provided in Appendix B).
- 3) Those participants who are randomized to the active control condition (Document This!) will also be asked to take 2 photographs each day using a Smartphone and to upload their pictures daily to a drive accessed by study staff. Rather than focusing on and capturing a photo of stimuli that evokes positive emotion, however, they will be directed to take pictures of things in their lives or surroundings that are representative of a “day in the life”. Like the participants in the Picture This! and Picture This! Plus Social Sharing Groups, they will also be asked to complete an online exercise each evening in which they review their documentary photos each evening and also asked to complete a series of questions via an internet survey.
- 4) Finally, participants randomized to the passive control group will NOT be directed to take any pictures during the 3 week intervention period.

All research participants in all 4 groups will be asked to complete a weekly online survey asking about whether they shared the pictures they took as a part of the study or as a part of their regular life (see Appendix F).

At the end of the intervention, all subjects will be provided a list of local mental health resources and will also be provided with the instructions for all 3 picture taking conditions (should they wish to implement any of the other exercises on their own time).

2. Identification of Subjects:

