In brief, both the Picture This! and the Picture This! Plus Social Sharing groups groups will be asked to utilize their Smartphones to take photographs on a daily basis for 21 days. The participants in the Picture This! and Picture This! Plus Social Sharing Group are asked to notice and then photograph events/situations/people/places/cues that elicit positive emotion (i.e., joy, awe, gratitude). They are asked to take at least two photographs each day. Participants in the active Document This! control group are also asked to take at least two photographs each day for 21 days that they feel is a good representation of their daily lives. The passive control group is not asked to take any pictures over the 21 day period. Each day, participants in the active conditions are asked to upload the photographs taken that day to a Google Drive accessed only by study staff. Participants will not have access to other participants' photographs, only their own. Participants will be informed in the consent form that submission of photographs poses a risk to confidentiality because the photos may include "self-shots" (photos they have taken of themselves) or photos of other things that could be linked back to them personally if by chance the trained and ethically-bound research assistants happen to know the participants.

At the conclusion of the study, participants will be asked in a separate Photo Release Form if they would provide permission to study personnel to use their photographs in research manuscripts, grant proposals, educational presentations, and other media presentations (see Appendix E).

All 4 groups are asked to provide an active email address and instructed to complete a short series of questions nightly that will be emailed to them from our lab email Gmail address. The email will include a link to a survey powered by Google Docs, which includes the MDES, modified to ask participants about feelings experienced during the past 24 hours (see above for description), and 6-9 additional questions designed specifically for this study (see Appendix D for questionnaires designed for both the active and control groups). The 3 active condition groups are also asked to complete a nightly savoring exercise and to answer several questions about the exercise via a link to the exercise sent to their email (see Appendix D).

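### H5b claims a shift in attention but is tested only on group level, so a difference could reflect the arm-specific photo instructions

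*Combined protocol and SAP*

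**What the plan says.** Under Mediators of Change, H5 states that the PT and PTPSS arms "will demonstrate significant changes in behavioral indicators of attentional shifts". H5a concerns the number of photographs over the course of the intervention. H5b says that these participants "will include more social behavior as the focal point".

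The analysis paragraph after H7 treats the two parts differently. For H5b: "H5b and H6 are straightforward between-groups analyses, for which we will use ANOVA to test for significant differences between groups". For H5a: "H1-H3 and H5a will be tested using mixed-factor ANOVA". H5b is not in the second list.

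On what the arms photograph, section 3 (Testing Procedure) says that PT and PTPSS participants are "asked to notice and then photograph events/situations/people/places/cues that elicit positive emotion". In the opening description of the conditions, item 3 says of Document This! that "they will be directed to take pictures of things in their lives or surroundings that are representative of a" typical day. Section 3 also says that instruction packets are handed over and reviewed at randomisation, that PTPSS participants show their pictures in person to someone each week, and that the passive control arm has no picture-taking task.

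The closing paragraph of the protocol adds that the daily photographs may be scored for positivity and social connection, that these may rise over time, and that exploratory growth curve analyses will be run. It cross-refers to H5a.

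**The concern.** Change and shift are statements about time, whereas the named H5b test compares groups on level. The photo arms have different subject-matter instructions before anyone takes a study photograph, so social content could differ from the first day for reasons unrelated to a developing change in attention. PTPSS has a further possible reason, because its participants know that each week's pictures will be shown to someone. No photographs from before the instructions are described that could serve as a baseline, and the only comparator with photographs follows a different instruction.

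At stake is the interpretation of one behavioural indicator. A significant H5b could be reported as evidence for the attentional mechanism although the planned test cannot tell that mechanism from compliance with the task.

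**Working it through.** **Claim against test.** The plan gives no figure for H5b to reproduce: no alpha, SD, effect size or allocation ratio. The first step is therefore textual.

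| Item | H5a | H5b |
|---|---|---|
| Outcome | number of photographs | social behaviour as focal point |
| Over-time wording in the hypothesis | yes | only through the H5 stem |
| Planned test | mixed-factor ANOVA | between-groups ANOVA |
| Time factor in the named test | within-subject factor | none |

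A comparison of level gives the same answer whether the arms differ by a constant amount from day 1 or drift apart over 21 days. It cannot separate the two.

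**Illustration 1: pooled contrast.** Inputs: about 240 recruits and four arms (from the protocol); equal allocation, so 240/4 = 60 per arm, no dropout, two-sided 0.05, and an instruction effect of 0.25 to 0.5 SD that is constant from day 1 (all assumed).

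- SE of the standardised difference, 120 v 60: sqrt(1/120 + 1/60) = sqrt(0.025) = 0.158.
- At 0.25 SD: 0.25/0.158 = 1.58; P(Z > 1.96 − 1.58) = P(Z > 0.38) = 0.35.
- At 0.5 SD: 0.5/0.158 = 3.16; P(Z > 1.96 − 3.16) = P(Z > −1.20) = 0.885, or about 88%.

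**Illustration 2: simulation.** Assumed: three photo arms of 60, 21 days, two photographs a day, a yes/no social focal point, person-to-person SD of 0.7 or 1.0 on the logit scale, an instruction effect constant from day 1, no trend in any arm, and 1,500 trials per setting. The level test is a one-way ANOVA on person means. The time test is a one-way ANOVA on person-level day slopes. Shares are for a typical participant. Cells give the fraction of trials significant at 0.05, for SD 0.7 / SD 1.0.

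| Control share | PT and PTPSS share | Level test | Time test |
|---|---|---|---|
| 20% | 20% | 0.049 / 0.051 | 0.054 / 0.048 |
| 20% | 25% | 0.505 / 0.267 | 0.047 / 0.041 |
| 20% | 30% | 0.963 / 0.784 | 0.057 / 0.051 |
| 20% | 35% | 1.000 / 0.977 | 0.035 / 0.051 |

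A constant instruction effect therefore makes the level test significant in 27% to 100% of trials, while the time test stays near 5%.

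**Price of a change measure.** At the minimum of two photographs a day there are 14 in a week and 42 overall. For independent photographs with a constant probability p, the sampling variance of a person's overall share is p(1−p)/42. For week 3 minus week 1 it is 2p(1−p)/14 = p(1−p)/7, six times as large. Stable differences between people cancel in the change score, which offsets part of this.

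**The case against.** Several points on the other side are sound.

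- **The plan does not ignore change over time.** The closing paragraph foresees scoring social connection in the daily photographs and fitting growth curves. This stands, but the scoring is optional, the models are exploratory, and the cross-reference goes to H5a, which is about counts. It does not replace the named H5b test.
- **The instructions are part of the intervention.** The stated aim is to retrain attention, and week 1 is already on treatment. A week 1 v week 3 test could miss an early shift, and a slope does not exclude growing compliance. Both limits stand, and they are reasons to keep the level comparison alongside the new test.

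Three stronger readings are tempting, and the documents do not support them.

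- *PT was told to photograph people and Document This! was told to photograph things.* That contrast joins two different sections. In the opening description, PT photographs something that brings joy or peace, with no mention of people. In section 3, Document This! photographs what represents daily life, without restriction to things. Where people are named, they are one of five listed subjects, and the outcome is social behaviour. The full instructions are in Appendix A, which is not available here. Compliance is a sufficient alternative explanation, not a demonstrated one.
- *The test has an inflated type I error.* It does not, for the effect of assignment. Under randomisation a difference caused by instructions is real; only its reading as an attentional shift is unsupported.
- *The trial cannot answer its question about attention.* The computerised attentional bias task is given at baseline and exit and is tested under H3. The mediation hypothesis, H4, refers to those cognitive processes and not to H5b.

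**Conclusion.** The mismatch is real and limited in scope. H5 speaks of change, but H5b is tested on level alone, in arms that received different instructions before the first photograph. A significant result would show an effect of assignment on what people photograph. It would not by itself show that attention shifted.

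The textual mismatch needs no numerical assumption. Its practical size cannot be derived from the documents. The 35% to 88% and 27% to 100% ranges depend on assumed instruction effects, equal allocation and no dropout; the first also depends on pooling PT with PTPSS. They show that the problem could matter, not how large it is. The tests of H1 and H3 are unaffected, so this is a correction worth making to one mechanism hypothesis and not a flaw in the trial as a whole.

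**What to change.** 1. In the analysis paragraph after H7, make the H5b test of change a condition-by-time test of each participant's proportion of photographs with a social focal point, in the three photo arms. Use week 1 v week 3 or a day slope, and choose before the photographs are coded. Define the time factor explicitly: the mixed-factor sentence takes a pre-intervention measure as its within-subject factor, and none is described for photographs, so adding H5b to that list would not be enough.
2. Keep the between-groups level comparison. Report it as an effect of assignment or a manipulation check and not, on its own, as evidence of an attentional shift.
3. State that the computerised attentional bias task under H3 carries the main attentional claim.
4. In the closing paragraph, point the sentence on social connection over time to H5b.

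The cost is analysis wording only. The same photographs are coded, and daily uploading supplies the dates as far as participants upload on the day. The downsides are a noisier measure, a possible miss of a shift within the first days, and no protection against growing compliance.

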Subjects must freely volunteer to participate. No coercion, implicit or otherwise, is permitted. Describe how potential subjects will be identified and approached (e.g., in class, door to door solicitation, through an ad, etc.). If the contact will be made in person, provide the statement that will be made orally to the potential subject(s). If the contact will be made in writing, submit a copy of the written communication text with this application.

Approximately **240** potential participants will be recruited at Clark University **and at other universities in the larger Worcester community** via flyering around campus as well as around Worcester in off campus public locations, email announcements, in-class announcements, **electronic advertisement boards** and via the Clark psychology subject pool. We would also like to post the contents of the flyers on a Facebook page created for the LEAF lab **as well as [name] website hosted by Clark. In order to extend recruitment beyond Clark, we will attempt to contact officials at other local universities to determine whether they will allow recruitment on their campuses and will follow their guidelines regarding local IRB approval, posting flyers on campus, email blasts, postings on electronic advertisement boards. Upon approval on other campuses, we would use all of the aforementioned resources (flyers on campus, emails, etc.) as appropriate.**

Interested students will be screened for eligibility **either in person or over the phone** (See Appendix C). If eligible, they will be schedule for an appointment, consented, asked to complete a series of questionnaires **and 2 computer tasks**, and then randomly assigned to **1 of 4 groups**.

There is no deceit involved in the study.

3. Testing Procedure:

Outline the testing procedure in sufficient detail to permit the Committee's assessment of potential psychological or physical implications (e.g. length of experiment, possible deception, physical or psychological discomfort). Attach a copy of any questionnaire or written test to be used in the study. For interviews, provide a copy of the interview questions to be used. Some research may be exempted, upon

review, from the IRB. A list of possible exempted research is available on this web page link. If you state that "minimal risk" may occur, please explain why (i.e. subject matter covered, the way responses are gathered, etc.)

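### The ANOVA for H5b and H6 fixes neither the unit of analysis (photograph or participant) nor whether 'more social behavior' is a count or a share

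*Combined protocol and SAP*

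**What the plan says.** The combined protocol and SAP gives the analysis of H5b and H6 in one sentence, in the analysis paragraph after H7 (Supplementary Analyses): "H5b and H6 are straightforward between-groups analyses, for which we will use ANOVA to test for significant differences between groups". The same paragraph sends H1 to H3 and H5a to a mixed-factor ANOVA with condition as the between-subjects factor.

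H5 (Mediators of Change) has two parts. Part (a) predicts that the experimental arms take increasingly more photographs as the intervention proceeds. Part (b) predicts that they "b) will include more social behavior as the focal point". H6, labelled exploratory, concerns photographic content, including positivity as judged by independent raters, and how it changes over the intervention.

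On the amount of data, section 3 (Testing Procedure) says that the two savoring arms "will be asked to utilize their Smartphones to take photographs on a daily basis for 21 days" and "They are asked to take at least two photographs each day". Document This! participants "are also asked to take at least two photographs each day for 21 days". For the fourth arm, "The passive control group is not asked to take any pictures over the 21 day period". The closing paragraph of the document adds exploratory growth curve analyses and says the daily photographs may be quantified for positivity and social connection, but it gives no model.

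The plan does not state the unit of analysis for H5b or H6, a per-participant summary, a participant effect, or whether H5b is counted or expressed as a share.

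**The concern.** Whether social behavior is the focal point, and how positive a picture looks, are properties of a single photograph. Each participant supplies many, and photographs by one person are likely to resemble each other. A one-way ANOVA assumes independent observations. It is sound when each participant contributes one value. It is unsound when each photograph is a separate observation, because the error term is then too small.

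A second gap remains even when the participant is the unit. Part (b) of H5 can be read as the number of social photographs or as their share. A number rises whenever a participant takes more photographs, and H5a predicts exactly that in the experimental arms. On a count, H5b could be confirmed with no shift in what participants attend to, so it would partly repeat H5a.

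A third gap concerns H6. It is about change over the intervention, and a between-groups ANOVA without a time term does not test change.

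**Working it through.** **Inputs from the document.** Photographs per participant: at least 2 per day x 21 days = 42 requested. Arms supplying photographs: 3 of 4. Total recruitment: "Approximately 240 potential participants will be recruited at Clark University".

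**Inputs assumed, because the document does not give them.** Equal allocation, so 240 / 4 = 60 per arm; alpha 0.05; full compliance with the 42; ICC of photograph scores within a participant, taken over a range; a 30% social share for the count check. The plan has no figure of its own to reproduce here.

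**1. Photograph as the unit.** The design effect is DEFF = 1 + (42 - 1) x ICC. With three arms (2 degrees of freedom, 180 x 42 = 7,560 photographs, F critical value about 3.00), the false-positive rate is about P(chi-square with 2 df > 2 x 3.00 / DEFF).

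| ICC | DEFF | Rate, three arms | Simulated (2,000 runs) |
|---|---|---|---|
| 0.02 | 1.82 | 19% | 18.6% |
| 0.05 | 3.05 | 37% | 35.8% |
| 0.10 | 5.10 | 56% | 53.9% |
| 0.20 | 9.20 | 72% | 71.6% |

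The rate passes 50% when DEFF reaches 4.32, that is at ICC = 3.32 / 41 = 0.08. For a contrast of two arms the rates are lower: 26% at ICC 0.05, 38.5% at 0.10 and 52% at 0.20, passing 50% at an ICC of about 0.18. With 21 photographs each (half compliance), the three-arm rate at ICC 0.10 is 37%.

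**2. Participant mean or share as the unit.** The same simulations analysed on one mean per participant gave 4.8% to 6.0% for three arms and 4.4% to 6.1% for two arms, over ICC 0 to 0.3. This analysis is valid.

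**3. Participant count as the unit for H5b.** Hold the share at 30% in every arm and set ICC at 0.1. The mean count is 0.3m, and its variance is m x 0.3 x 0.7 x [1 + (m - 1) x 0.1].

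- m = 42: mean 12.6, variance 42 x 0.21 x 5.1 = 44.98
- m = 46: mean 13.8, variance 46 x 0.21 x 5.5 = 53.13
- m = 55: mean 16.5, variance 55 x 0.21 x 6.4 = 73.92

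Let the control arm take 42 and both experimental arms the larger number. The noncentrality is 60 x (sum of squared deviations of the arm means) / (average variance).

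- 42 v 46: 60 x 0.96 / 50.41 = 1.14. The noncentral F with 2 and 177 df then gives about 14% significant.
- 42 v 55: 60 x 10.14 / 64.27 = 9.47, which gives about 79%. Simulation agrees, at about 80%.

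Analysed as shares, the same data give about 5%. The count result depends on the ICC as well as the gap: for two arms at 42 v 55 it is about 95% at ICC 0.05 and 53% at ICC 0.2.

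**The case against.** The strongest defence is that the plan never makes the photograph the unit. It calls these between-groups analyses, and the same paragraph names condition as a between-subjects factor for the other hypotheses. The natural reading is one score per participant, and on that reading the false-positive rate is about 5%. This stands. A reader might infer that the planned ANOVA has a false-positive rate above 50%. The documents do not support that: it needs the photograph as unit, an ICC of about 0.08 or more (three arms) or 0.18 or more (two arms), and full compliance. The document states no ICC and no alpha, and 42 is a requested minimum, not an achieved count.

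A reader might also infer that uneven photo numbers invalidate an ANOVA on participant shares. They do not. With 15% of participants supplying only 2 to 10 photographs, simulated rejection stayed at 4.9% to 5.6%. Unweighted means lose some precision (4% to 27% more variance under that assumed pattern), which affects power only.

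The count problem depends on the gap in photo numbers. The document gives no expected gap, and about 10% more photographs (42 v 46) gives only about 14%. Nor does any text say that raw totals will be used. Both points stand, but the ambiguity remains, and H5a makes some gap an expectation of the plan itself.

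The growth curves in the closing paragraph could address repeated photographs. They are exploratory and unspecified, and they do not replace the ANOVA named for H5b and H6.

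**Conclusion.** The concern holds as a gap in specification that has consequences. The plan leaves open three analyses of H5b. The most natural, a share per participant, is sound. An ANOVA on photographs is not: about 19% false positives at ICC 0.02, 37% at 0.05 and 56% at 0.10. A count per participant can turn a rise in photo numbers into an apparent social effect: at ICC 0.1, about 14% significant for 42 v 46 photos and about 80% for 42 v 55. For H6 the choice of unit is equally open, and the named ANOVA does not address change over time.

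Only the 42 comes from the document. The figures otherwise rest on the assumed 60 per arm, alpha, compliance, ICC, social share and photo gap.

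The importance is secondary. H6 is exploratory. H5b is a mechanism hypothesis, not a main outcome, and it is not the only behavioural evidence on mechanism, since H3 uses the computer tasks.

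**What to change.** Amend the analysis paragraph before the photographs are rated:

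- Define the H5b outcome as the share of a participant's photographs in which social behavior is the focal point.
- State that H5b and H6 compare the three photo arms.
- Analyse photographs with a mixed model that has condition as a fixed effect and a participant random intercept: logistic for H5b, linear for rated positivity in H6. Alternatively, keep ANOVA and apply it to one share or mean per participant.
- For H6, add time and a condition-by-time term. If ANOVA is kept for H6, the value per participant must itself be a measure of change.

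Either route excludes both the photograph-level and the raw-count readings. The cost is a few lines of text and slightly more analysis work. The ratings are the same and no new data are needed.
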